**9. Study Population**

**9.1.** Inclusion criteria for each subject population (e.g., patients, parents, providers):

**Aim 1:**

**Parents:** Parents of children who sustained a closed head injury and sought care in the Seattle Children's Hospital Emergency Department or Urgent Care within the past 2 years.

**Children:** Children of parent participants chosen for the study using the criteria immediately above. Please note: Children will have no active participation in the study, but private identifiable information about them will be collected.

**Medical providers:** Medical providers (physicians and nurses) who have provided post-closed head injury care in the Seattle Children's Hospital Emergency Department.

**Aims 2 and 3:**

**Parents:** Parents of children who sustained a closed head injury and sought care in the Seattle Children's Hospital Emergency Department or Urgent Care during the study period.

**Children:** Children aged 5-17 of parent participants chosen for the study using the criteria immediately above.

Please note: Children will have no active participation in the study, but private identifiable information about them will be collected.

**Aim 4:** (1) Cognitive interview: Parents of children who sought care (for any reason) in the Seattle Children's Hospital Emergency Department or Urgent Care during the study period; (2) Online surveys: English-speaking parents (age 18 and older)

**9.2. Exclusion criteria for each subject population:**

**Parents:** Not fluent in English or Spanish

**Medical providers:** Not fluent in English

**9.3. Populations with special considerations, involved in the study:**

Children/Teenagers

Risk assessment specific to this vulnerable population and additional safeguards:

Private and potentially identifiable data will be collected about child patients. Child patients will provide verbal or written assent for study participation in Aims 1, 2, and 3.

Children who are Wards of the State

Risk assessment specific to this vulnerable population and additional safeguards:

N/A

Adults Unable to Consent

Risk assessment specific to this vulnerable population and additional safeguards:

N/A

Neonates of Uncertain Viability or Non-Viable Neonates

Risk assessment specific to this vulnerable population and additional safeguards:

N/A

Pregnant Women

Additional safeguards:

N/A

Prisoners

Additional safeguards:

N/A

Economically or educationally disadvantaged persons

Additional safeguards:

N/A

## 10. Number of Subjects

### 10.1. Total number of subjects to be enrolled locally:

**Aim 1:** We anticipate recruiting and consenting about 20 parents, 20 children and 20 healthcare providers.

**Aim 2:** We anticipate recruiting and consenting about 200 parents and 200 children

**Aim 3:** We anticipate recruiting and consenting about 200 parents and 200 children

**Aim 4:** (1) Cognitive interviews: We anticipate recruiting at least 10 parents for cognitive interviews; (2) Online survey: We anticipate recruiting at least 700 participants for the online surveys.

### 10.2. Total number of subjects to be enrolled across all participating sites:

N/A

### 10.3. Number of screened subjects versus the actual number enrolled in the research:

**Aim 1:** We estimate we will need to screen 60 parents to enroll 20 parent participants, and 25 healthcare providers to enroll 20 participants.

**Aim 2:** We estimate that we will need to screen 600 families to enroll 200 eligible parents

**Aim 3:** We estimate that we will need to screen 600 families to enroll 200 eligible parents.

**Aim 4:** (1) Cognitive interviews: We estimate that we will need to screen 30 families to enroll 10 parent participants; (2) Online surveys: We estimate that we will need to screen 800 parents to enroll 700 parent participants.

### 10.4. Power analysis:

**Aim 1:** This is a qualitative study and thus a power calculation is not appropriate.

**Aims 2 and 3:** With 200 participants per group (Aim 2 and Aim 3), we will have  $\geq 98\%$  power to detect a meaningful 20% difference in the proportion of parents receiving each specific component of the reach measure (Table 1), in Aim 2 vs. Aim 3 groups, after allowing for 10% attrition ( $\alpha=0.05$ ). For Health Literacy subgroup comparisons, we will have  $\geq 80\%$  power to detect a 20% difference, assuming 10% attrition.

**Aim 4:** This is an exploratory, primarily qualitative study and thus a power calculation is not appropriate.

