randomized to either the education toolkit intervention condition or treatment-as-usual control condition in a 2:1 ratio. For participants in the control group (Aim 2 and those randomized to control group in Aim 3), there will be no change to the nature of provider communication with families about closed head injury/concussion. Data will be collected about the experience that family's have seeking care in the ED for their child's closed head injury. For both Aims 2 and 3, survey data will be collected from parents at three time points: at initial ED visit before discharge, one day post-visit, and at 2-week follow-up. As part of parent data collection for Aims 2 and 3, all parents will complete the 3-item Brief Health Literacy Screen at the first time point of survey data collection. Please see timeline (uploaded in "Other Attachments" for more information regarding the timing of Aims 2 and 3.

For Aim 3 participants randomized to the intervention group, the parent education toolkit finalized in Aim 1 will be delivered by the study team. Based on feedback from qualitative interviews in Aim 1, the toolkit will consist of brief education from a member of the ED study team at enrollment, followed by asynchronous phone-based follow-up (audio/ voice and/or text). Parents will receive automated daily educational messages related to how they can provide recovery support to their children during the 2-week study period. Automated messages will be delivered via Twilio, by turning on the "initiate survey as SMS conversation" feature in REDCap. Parents will also receive reminders to schedule a follow-up appointment, with an option to receive tailored support from research staff to help with scheduling. A more detailed description and content of each toolkit component can be found in "Aim 3 Parent Education Toolkit Content" uploaded in "Other Attachments".

All patient materials will be available in both English and Spanish. Certified translations will be uploaded prior to use.

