### 5.4. Data to be collected, including long-term follow-up data:

**Aim 1:** The goal of the parent interview will be to (1) explore their experiences with communication in the ED following their child's concussion and (2) provide critical feedback on the content and design of the CDC ACE Care Plan. The Cultural Treatment Adaptation Framework, will provide the foundation for the open-ended question guide for parents, with questions about the handout focusing on: (1) language and semantics, (2) use of culturally relevant examples, and 3) preferences for material delivery. The goal of the healthcare provider interviews will be to review the CDC ACE Care Plan handout and the RED Toolkit, and provide feedback about (1) barriers and facilitators to implementation in the ED and (2) the type of support (e.g., materials, training) that they believe would be helpful for implementation. CFIR^24 will provide the foundation for the open-ended question guide for healthcare providers, with a focus on individual characteristics (e.g., provider knowledge and self-efficacy), implementation toolkit characteristics, and aspects of the inner setting (e.g., time pressures in the busy ED, compatibility with existing communication networks and tools such as the EHR system) that may constrain implementation success.

**Aims 2 and 3:** Survey data will be collected from up to 200 parents at three time points: at initial ED visit before discharge, one day post-visit, and at 2-week follow-up. **Primary outcome.** Our primary outcome will be parenting behaviors at 2 week follow-up (emotional support and instrumental support). **Secondary outcomes.** Parent surveys at initial ED visit before discharge, one day post-visit, and two-weeks post visit will assess parent cognitions related to concussion management and proximal cognitions (concussion management knowledge and self-efficacy), parental anxiety related to concussion management, youth outcomes (health-related quality of life, post-concussion symptoms), the nature of provider-parent communication in the ED (e.g., did the parent have an opportunity to ask questions?), and additional

covariates (demographics and environmental conditions). In Aim 3 only, the parent surveys at 2 weeks post-visit will also include questions about their experiences with receiving the education toolkit.

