**Aims 2 and 3: Primary outcomes.** We will compare parenting behaviors (emotional support and instrumental support) at Time 3 between the two groups using chi-squared tests for each behavior and total proportion of behaviors. **Secondary outcomes.** For each group (control and intervention), the percentage of parents reporting receipt of specific discharge components will be calculated and compared. We will also compare rates across specific subgroups, including high vs. low health literacy parents and between parents who speak English at home vs. those who do not. These percentages will be compared across subgroups using chi-squared tests to assess statistical significance. We will also compare characteristics of subjects who (a) agree to participate vs. those who do not, and (b) participate throughout follow-up vs. any lost to follow-up. We will also conduct exploratory analyses of the mean change in parent cognitions related to concussion management (concussion management knowledge, parental anxiety, and behavioral self-efficacy) and child well-being scores (child PEDs-QL and PCSI) from Time 1 to Time 3, between the groups using t-tests, and plotting trajectories for each group. We will adjust analyses for child age, sex, baseline post-concussion symptoms/severity, as well as covariates not determined to be effect modifiers, if associated with outcome and distributions vary by treatment group. Missing data will be examined for patterns with covariates, sensitivity analyses used to assess impact of missing data on results and imputation used as appropriate to address missingness. **Parent experiences with enhanced education.** Survey data will be analyzed descriptively, with associations by insurance status, language, and gender assessed. For qualitative data, audio-recorded and transcribed interviews will be coded using a deductive content analytic approach using consensual qualitative research methods. First, two independent coders will review each interview transcript, applying codes from the CFIR, Communication Accommodation Theory, and USE-EBPI while remaining open to other emergent themes. They will then compare codes and agree on final codes using a process of deliberation and consensus.

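### The power statement in 10.4 covers groups and an outcome that the primary analysis does not use: planned control vs intervention has about 95% power at worst, not at least 98%, and the primary outcome has none stated

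*Combined protocol and SAP*

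**What the plan says.** Section 10.4 (Power analysis) starts from two equal groups: "With 200 participants per group (Aim 2 and Aim 3"). It claims at least 98% power for a 20% "difference in the proportion of parents receiving each specific component of the reach measure (Table 1), in Aim 2 vs. Aim 3 groups", at alpha 0.05 after 10% attrition. No base rate is given.

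Section 5.2 (Research procedures) describes a different structure. The whole Aim 2 cohort is control. Aim 3 parents are "randomized to either the education toolkit intervention condition or treatment-as-usual control condition in a 2:1 ratio". The control group is then defined across both cohorts: "For participants in the control group (Aim 2 and those randomized to control group in Aim 3").

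Section 5.4 names the primary outcome: "Our primary outcome will be parenting behaviors at 2 week follow-up (emotional support and instrumental support"). Section 14.1 analyses it in the same terms: "We will compare parenting behaviors (emotional support and instrumental support) at Time 3 between the two groups using chi-squared tests for each behavior". Receipt of discharge components appears in 14.1 under secondary outcomes: "For each group (control and intervention), the percentage of parents reporting receipt of specific discharge components will be calculated and compared".

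**The concern.** There are two mismatches.

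- **Groups.** Section 10.4 treats the Aim 3 cohort as if it were the intervention arm. About a third of that cohort receives usual care, and 14.1 compares control with intervention, not one cohort with the other. The stated power therefore belongs to no comparison in the analysis plan.
- **Outcome.** Section 10.4 concerns a reach measure. The nearest item in 14.1 is receipt of discharge components, which is secondary. The outcome on which the trial will be judged has no power statement.

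A reader cannot learn from 10.4 what the primary comparison can detect. The gap matters more because the note on the title page says the analysis was simplified to focus on primary outcomes after a smaller sample was recruited. The outcome that was kept is the one that was never powered.

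**Working it through.** **Inputs from the documents**
- 200 parents in each of Aims 2 and 3 (3.1, 10.1, 10.3).
- Aim 3 randomised 2:1, with control defined as Aim 2 plus the Aim 3 controls (5.2).
- 20% difference, 10% attrition, alpha 0.05 (10.4).
- Chi-squared tests (14.1).

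**Assumptions**
- The 20% is 20 percentage points in one binary item.
- The test is two-sided, without continuity correction.
- The control rate *p* is not stated, so values from 10% to 70% are scanned.

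**Group sizes**
- Aim 3 intervention: 200 × 2/3 ≈ 133, and × 0.9 = 120.
- Aim 3 control: 200 × 1/3 ≈ 67, and × 0.9 = 60.
- All controls: 200 + 67 = 267, and × 0.9 = 240.
- Each whole cohort: 200 × 0.9 = 180.

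**Formula**

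Power = Φ[(|p₂ − p₁| − 1.96·SE₀) / SE₁], where
- SE₀ = √[p̄(1 − p̄)(1/n₁ + 1/n₂)], with p̄ the weighted mean rate;
- SE₁ = √[p₁(1 − p₁)/n₁ + p₂(1 − p₂)/n₂].

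**Step 1: the plan's own figure, 180 vs 180.** At 40% vs 60%, p̄ = 0.500, SE₀ = 0.0527 and SE₁ = 0.0516. Then (0.20 − 1.96 × 0.0527)/0.0516 = 1.87, which gives 96.9%. This is the least favourable base rate. Power is 98.7% at control rates of 20% and 60%, and 99.8% at 10% and 70%. Without attrition, 200 vs 200 gives 98.1% at worst. The stated 98% is therefore reproduced to within about a point for the groups that 10.4 assumes.

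**Step 2: control vs intervention as defined, 240 vs 120.** At 40% vs 60%, p̄ = 0.467, SE₀ = 0.0558 and SE₁ = 0.0548. Then (0.20 − 1.96 × 0.0558)/0.0548 = 1.66, which gives 95.1%.

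**Step 3: randomised Aim 3 parents only, 60 vs 120.** At 40% vs 60%, p̄ = 0.533, SE₀ = 0.0789 and SE₁ = 0.0775. Then (0.20 − 1.96 × 0.0789)/0.0775 = 0.59, which gives 72.1%.

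| Control rate | 180 vs 180 | 240 vs 120 | 60 vs 120 |
|---|---|---|---|
| 10% | 99.8% | 99.5% | 88.7% |
| 20% | 98.7% | 97.7% | 78.5% |
| 30% | 97.5% | 95.9% | 73.3% |
| 40% | 96.9% | 95.1% | 72.1% |
| 50% | 97.5% | 95.8% | 74.5% |
| 60% | 98.7% | 97.7% | 80.6% |
| 70% | 99.8% | 99.6% | 90.3% |

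The 240 vs 120 contrast is below 98% for control rates of about 19% to 61%. The 60 vs 120 contrast is below 75% for about 26% to 51%. With rates near 50%, 80% power needs about 16 points for 240 vs 120 and about 22 points for 60 vs 120.

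**Step 4: 10.4 taken literally.** If the toolkit adds 20 points, the whole Aim 3 cohort has rate (2/3)(p + 0.20) + (1/3)p = p + 0.133. A 180 vs 180 comparison of 13.3 points has 92.8% power at a control rate of 10%, 71.9% at 40% and 85.2% at 70%, with a minimum of 71.7% near 43%.

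**Simulation check.** With 400,000 runs of the chi-squared test at 40% vs 60%, 240 vs 120 gives 94.9% and 60 vs 120 gives 72.4%. The diluted 180 vs 180 case gives 72.4%.

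**The case against.** The strongest reply is that little changes in practice. The comparison the plan defines keeps 95% power or more for a 20-point difference in one item at every control rate scanned. Part of the shortfall is not due to the allocation either: 10.4's own groups give 96.9% at 40% vs 60%. Of the 2.9-point gap between 98% and 95.1%, about 1.1 points are present before the 2:1 split enters, and about 1.8 come from the split. This stands. The defect is mainly one of wrong groups and wrong outcome, and the numerical loss for the pooled contrast is small.

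The lower figures also belong to contrasts that the analysis plan does not name. That is true of the randomised-only comparison. Its power is still worth stating, because 200 of about 267 pooled controls come from an earlier cohort that was not randomised, and only the comparison within Aim 3 is protected by randomisation. The diluted figure shows only what 10.4 would mean if read literally.

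Three cautions also stand:
- Worst means worst over base rates under the listed assumptions. With a continuity correction, 240 vs 120 gives 93.8%.
- Section 5.4 speaks of up to 200 parents. If that meant the total, split equally between the aims, the pooled contrast would be about 120 vs 60, with about 72% at worst.
- Table 1 is not in the text available, so equating the reach measure with receipt of discharge components is an inference. Whatever Table 1 contains, 10.4 does not mention parenting behaviours.

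**Conclusion.** The point holds and should be fixed. The 98% in 10.4 describes neither the planned contrast nor the primary outcome.

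For control vs intervention as the protocol defines it, 98% overstates power by up to about 3 points at mid-range base rates. The planned comparison is not invalidated. The randomised comparison alone would miss a 20-point difference more than one time in four at control rates of about 26% to 51%.

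These results rest on 200 parents per aim, 10% attrition, an uncorrected two-sided test and an assumed base rate. The 20-point effect is stated only for reach, so none of the figures is power for parenting behaviours; that cannot be computed from the documents. Nor can achieved power, since the title-page note gives no number for the smaller sample.

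**What to change.** In 10.4, delete the Aim 2 vs Aim 3 figure, name the contrast to be tested and state the assumed base rate. Suggested text, labelled as power for the planned sample and for a single binary item:

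> Intervention (about 133) vs control (Aim 2 plus Aim 3 controls, about 267); after 10% attrition, about 120 vs 240. With an assumed control rate of 40%, power for a 20-point difference is about 95% (two-sided 0.05). For the randomised Aim 3 comparison alone (about 120 vs 60), it is about 72%, and 80% power needs about 22 points.

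The 40% is illustrative and is the least favourable rate for the pooled contrast; the investigators should replace it if they have a better value. Then either give an effect size and base rate for parenting behaviours at 2 weeks, with the resulting power, or say plainly that none was specified.

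The cost is a text change and a less favourable stated power. No extra participants are needed and the analysis does not change.

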## 11. Withdrawal of Subjects

### 11.1. Anticipated circumstances under which subjects will be withdrawn from the research without their consent:

We do not anticipate circumstances under which participants will be withdrawn from the research without their consent

**11.2. Procedures for orderly termination:**

N/A

**11.3. Procedures that will be followed when subjects withdraw from the research, including partial withdrawal from procedures with continued data collection and withdrawal from data/biospecimen banking:**

Participants may withdraw from the study at any time by notifying study personnel. Once a participant expresses their desire to withdraw, the researcher will terminate data collection. The study team will review, on a case-by-case basis, whether partial data collected will be used in the analysis.

**12. Risks to Subjects****12.1. Reasonably foreseeable risks to subjects (include each study population, each arm, and optional procedures):**

This study involves no more than minimal risk to participants. Potential risks include the following:

Testing burden: participants may experience inconvenience associated with answering interview questions

Loss of confidentiality: participants will provide identifiable information about themselves, and in the case of parents, their child.

**12.2. Procedures with unforeseeable risks:**

N/A there are no procedures that pose unforeseeable risks.

**12.3. Procedures with risks to an embryo or fetus should the subject be or become pregnant:**

N/A there are no procedures that may have risks to an embryo or fetus should the subject be or become pregnant.

**12.4. Risks to others who are not subjects:**

N/A There are no risks to others who are not subjects.

**12.5. Procedures performed to lessen the probability or magnitude of risks:**

N/A- this is a minimal risk study

**13. Potential Benefits to Subjects****13.1. Potential benefits that individual subjects may experience from taking part in the research:**

There is no anticipated benefit of participating in this study. The information from this study could benefit children who sustain concussions in the future.

**14. Data Analysis/Management****14.1. Data analysis plan, including statistical procedures:**

**Aim 1:** Qualitative data will be digitally recorded and transcribed verbatim and coded for relevant themes using a thematic analysis approach. This analysis will begin with an intensive review of audio-recordings and coded transcripts by two experienced qualitative coders to identify themes across stakeholder groups

and settings. Coded segments will then be entered into Dedoose© software to facilitate analysis, and themes will be iteratively revised to better represent the overall tenor of the interviews, until a representative sample of themes has been developed that is independently supported by both coders. Interim analyses will be conducted after 5 interviews in each category, and themes that develop will be used to iterate provider support materials. We will explore whether there are emergent differences in groups of parents (e.g., differences by demographic variables) and healthcare providers (e.g., by provider type) and within family dyads. Data analysis will occur on an ongoing basis, with emergent results iteratively informing adaptations to the question guide so as to appropriately clarify and contextualize responses related to the target areas of questioning.

**Aims 2 and 3: Primary outcomes.** We will compare parenting behaviors (emotional support and instrumental support) at Time 3 between the two groups using chi-squared tests for each behavior and total proportion of behaviors. **Secondary outcomes.** For each group (control and intervention), the percentage of parents reporting receipt of specific discharge components will be calculated and compared. We will also compare rates across specific subgroups, including high vs. low health literacy parents and between parents who speak English at home vs. those who do not. These percentages will be compared across subgroups using chi-squared tests to assess statistical significance. We will also compare characteristics of subjects who (a) agree to participate vs. those who do not, and (b) participate throughout follow-up vs. any lost to follow-up. We will also conduct exploratory analyses of the mean change in parent cognitions related to concussion management (concussion management knowledge, parental anxiety, and behavioral self-efficacy) and child well-being scores (child PEDs-QL and PCSI) from Time 1 to Time 3, between the groups using t-tests, and plotting trajectories for each group. We will adjust analyses for child age, sex, baseline post-concussion symptoms/severity, as well as covariates not determined to be effect modifiers, if associated with outcome and distributions vary by treatment group. Missing data will be examined for patterns with covariates, sensitivity analyses used to assess impact of missing data on results and imputation used as appropriate to address missingness. **Parent experiences with enhanced education.** Survey data will be analyzed descriptively, with associations by insurance status, language, and gender assessed. For qualitative data, audio-recorded and transcribed interviews will be coded using a deductive content analytic approach using consensual qualitative research methods. First, two independent coders will review each interview transcript, applying codes from the CFIR, Communication Accommodation Theory, and USE-EBPI while remaining open to other emergent themes. They will then compare codes and agree on final codes using a process of deliberation and consensus.

**Aim 4:** (1) Cognitive interviews: Analysis will be conducted by reviewing parents' comments and responses to questions about the survey tool. We will explore if there are any emergent differences in understanding survey questions among groups of parents (low vs. high health literacy). Data analysis will occur on an ongoing basis, with emergent results iteratively informing adaptations to the question guide and the survey itself; (2) Online surveys: Survey responses will be reviewed with a focus on the psychometric properties of items and scales (e.g., how are responses distributed), with the plan to retain only items with adequate variability and normal or near-normal distribution. To limit redundancies in the final survey, we will conduct exploratory analyses to determine which survey questions are correlated. Finally, we will compare responses across key parent characteristics (e.g., age, gender, prior concussion) to determine whether psychometric properties are similar across groups.

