**Developing an implementation strategy for post-concussion communication with  
low health literacy parents in the emergency department**

**NCT Number:** NCT04112914

**Document Date:** 4/29/2021

*Please note: Due to the smaller sample recruited we simplified our analytic plan to focus on primary outcomes and no subgroup comparisons.*

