**Parent Interviews** (Aim 3 only): Based on parents' responses to their experiences with the education toolkit, a purposive recruitment strategy will be used to invite by email 12 parents to participate in one-on-one qualitative interviews. Interview content will be based on the Consolidated Framework for Implementation Research and Communication Accommodation Theory, assessing their experiences implementing content of the intervention, and their affective experience engaging with educators. Following best practice guidance for eliciting qualitative data about implementation barriers and facilitators and communication experiences, the question guide will remain open ended so that interviewers can explore other themes raised by participants.

**Aim 4:** (1) Cognitive interviews: The goal of the cognitive interview will be to assess understanding of survey questions and receive feedback on survey content. Research assistants will talk through questions with parents and identify 1) if question wording is confusing or challenging in any way, and 2) if questions could be asked in a way that is easier to understand. (2) Online surveys: The surveys will primarily assess parent behaviors, knowledge, and self-efficacy related to concussion management in order to validate our survey tool. Additional covariates (such as demographic information, previously diagnosed concussion) will also be collected for the purpose of ensuring the survey tool is valid and reliable for the general population. Survey questions will come from a bank of potential questions, which can be found in the support document "Aim 2 Parent Survey Questions".

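### Section 14.1 tests the primary outcome at least three ways, with no deciding test, success rule or multiplicity adjustment, and leaves the total undefined

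*Combined protocol and SAP*

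**What the plan says.** Section 5.4 defines the outcome: "Our primary outcome will be parenting behaviors at 2 week follow-up (emotional support and instrumental support"). Neither part is ranked above the other. Section 14.1, under a plural heading for primary outcomes, compares the groups "at Time 3 between the two groups using chi-squared tests for each behavior and total proportion of behaviors".

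Other places that might have settled the matter do not:
- Section 3.1, headed as endpoints, gives only recruitment targets and when participation ends.
- The hypothesis in 1.2 speaks of understanding and preparedness, and picks out no behaviour.
- The adjustment sentence in 14.1, "We will adjust analyses for child age, sex, baseline post-concussion symptoms/severity", concerns covariates, not the number of tests.
- Section 10.4 has the only alpha in the document, 0.05. It is stated for "the proportion of parents receiving each specific component of the reach measure", which is not the primary outcome.
- The number of behaviour items is not given. For the measure-validation surveys, 5.4 says: "Survey questions will come from a bank of potential questions, which can be found in the support document". That support document is not part of the file.
- The cover note says: "Due to the smaller sample recruited we simplified our analytic plan to focus on primary outcomes and no subgroup comparisons". It removes subgroup comparisons and adds no rule for the primary tests.

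**The concern.** With three or more tests labelled primary and no rule for reading them, a report could present whichever test reaches 0.05 as the primary finding. If any one result counts, the overall false-positive rate exceeds the rate of each test. The cover note narrows the analysis to primary outcomes, so the study's conclusion rests on these tests.

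The total adds a second gap. It is not defined as one value per parent, yet a chi-squared test is named for it. That test assumes independent observations, and several responses from one parent are not independent.

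**Working it through.** **The plan's own figure.** The document states no error rate for the primary tests. Its one power figure (10.4: at least 98% for a 20-point difference, 200 per group, 10% attrition, alpha 0.05) concerns the reach measure. With 200 × 0.9 = 180 per group, the two-proportion formula gives 96.9% for 40% vs 60% (the least favourable case), 98.7% for 20% vs 40% and 99.8% for 10% vs 30%. It reproduces closely, but it does not bear on this point.

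**Inputs.** From 5.4 and 14.1: two behaviours plus a total, so a minimum of three tests. Assumed: two-sided 0.05 per test (10.4 gives 0.05 for another measure), any one success counts, and correlation ρ between the two behaviour statistics from 0 to 0.9 (not given).

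**Model.** Under no effect, Z1 and Z2 are standard normal with correlation ρ. The total is T = (Z1 + Z2)/√(2 + 2ρ). The quantity wanted is P(|Z1| > 1.96 or |Z2| > 1.96 or |T| > 1.96), found by simulation with at least 2,000,000 draws per ρ.

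| ρ | any of three | benefit direction only | Holm or Bonferroni, smallest p ≤ 0.0167 |
|---|---|---|---|
| 0 | 11.5% | 5.8% | 4.1% |
| 0.3 | 10.5% | 5.3% | 3.8% |
| 0.5 | 9.7% | 4.8% | 3.4% |
| 0.7 | 8.6% | 4.3% | 3.1% |
| 0.9 | 7.1% | 3.5% | 2.5% |

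The benefit-only column compares with a nominal 2.5%. The two behaviours without the total already give 9.75% (1 − 0.95²) at ρ = 0 and 7.0% at 0.9. Three independent tests would give 1 − 0.95³ = 14.3%, but the total cannot be independent of its parts.

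**Check with binary data.** The settings were 120 vs 60, 120 vs 240 and 60 vs 30 parents, prevalences 0.5 and 0.7, and within-parent correlation 0 to 0.9. Chi-squared per behaviour plus a t-test on the parent-level total gave any-rejection rates of 6.4% to 11.7%. The t-test alone held 4.7% to 5.3%.

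**More items.** If each behaviour means each survey item, the rate rises. Independent tests would give 1 − 0.95⁵ = 22.6% for five and 1 − 0.95¹⁰ = 40.1% for ten, and less if items correlate.

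**The total.** Suppose two equally common responses per parent with correlation ρ were pooled as independent. The variance would be understated by a factor of 1 + ρ, so the true size is 2[1 − Φ(1.96/√(1 + ρ))]. This is 8.6% at 0.3, 11.0% at 0.5 and 15.5% at 0.9. Simulated binary trials agree.

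**Power under each remedy.** The assumption is 80% power per behaviour at 0.05 (non-centrality 2.80), ρ from 0 to 0.9.

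| Rule | both behaviours improve equally | only this behaviour improves |
|---|---|---|
| Holm across three | 71–77% | 66–67% |
| Total first, then each behaviour at 0.05 | 78–80% | 30–49% |

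**The case against.** The strongest reply is that the quantified harm depends on assumptions. The plan nowhere says that one significant result is success, states no alpha for these tests, and does not fix their number. All of that is true. A reader might infer that this plan has a 7% to 12% error rate. The document does not support that: the range belongs to one reading, with exactly three tests and a valid test of the total.

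Equal rank is also an interpretation. Section 5.4 uses the singular for the primary outcome, so a lead total with supporting component tests is conceivable. The document is silent on rank, and that silence is the gap.

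A reader might further infer that responses are pooled across behaviours. The document does not say so; the pooled figures only show why a definition is needed. Nor does the cover note show that a result was chosen after the data were seen. It reports a smaller sample and a simplified analysis.

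Two-sided rates count false positives in both directions, while the study expects improvement. The benefit-only rates are lower, but still above 2.5%.

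Finally, a rule added now may not be prespecified, and Holm costs power in a sample already smaller than planned. Both points stand. They bear on disclosure and on which rule to choose, not on whether a rule is needed.

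**Conclusion.** The omission is certain from the text: at least three primary tests and no way of deciding among them. Its size is conditional. If exactly three tests are each run at two-sided 0.05, the total is validly tested and any one result counts, the overall error is about 7% to 12% (3.5% to 5.8% for false claims of benefit). More separately tested items would raise it. One named deciding test, or Holm, brings it to 5% or below.

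**What to change.** In 14.1:

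1. List the behaviours to be tested. Define the total as one value per parent: the proportion of listed behaviours that the parent reports. Compare it by t-test, or by linear regression with the covariates already planned.
2. State one rule holding the overall two-sided error at 5%:
   - **Total first.** The parent-level total decides at 0.05, and each behaviour is tested at 0.05 only if the total succeeds. With two behaviours this holds 5%. If neither is affected, the total is not affected either; if only one is unaffected, only one false claim is possible. If more than two are tested separately, adjust among them (for example by Holm) after the total.
   - **Holm across all listed primary tests.** With three, compare the smallest p-value with 0.0167, the next with 0.025 and the last with 0.05, stopping at the first failure.
3. Report all primary tests with confidence intervals.
4. State whether the rule was set before Time 3 data were seen by group, because the cover note describes recruitment as past.

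The change is wording only and needs no new data. The cost is power. Holm takes a behaviour test from an assumed 80% to about 66–77%. Testing the total first costs little if both behaviours improve, but more than Holm if only one does. The investigators should choose according to the effect they expect. Under Holm, a single unadjusted p below 0.05 could no longer be claimed as a primary success; under the total-first rule, only the total's could.
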